7.2.2 Inclusion criteria

The patients are included if they meet all the following criteria:

1. Patients with a new prescription date (index date) for tedizolid (ATC code: J01XX11) or linezolid (ATC code: J01XX08) during the cohort entry period (21-Aug-2018 to 31-Mar-2025).

A new prescription for tedizolid or linezolid is defined based on Tables 2 and 3.

Includes all patients who have been prescribed the above medications, regardless of whether they are outpatients, inpatients, or emergency cases.

2. Primary analysis: Patients with confirmed diagnosis of MRSA (ICD-10: A49.0 and disease name notation: MRSA infection) and confirmed diagnosis of indications for both tedizolid and linezolid (1: Deep Skin Infections, Chronic Abscesses, 2: Secondary infection of trauma, burns, and surgical wounds) in the same month or previous month of the index date. The disease code list is provided as Appendix A.

Sensitivity analysis-1 (see Section 7.8.3 (4)): Patients with confirmed or suspected diagnosis of MRSA (ICD-10: A49.0 and disease name notation: MRSA infection) and confirmed diagnosis of indications for both tedizolid and linezolid (1: Deep Skin Infections, Chronic Abscesses, 2: Secondary infection of trauma, burns, and surgical wounds) in the same month or previous month of the index date. The disease code list is provided as Appendix A.

Sensitivity analysis-2 (see Section 7.8.3 (5)): Patients with confirmed or suspected / probable diagnosis of MRSA (ICD-10: A49.0 and disease name notation: MRSA infection, Staphylococcal infection, MRCNS infection, MSSA infection, MRSE infection, and Vancomycin-resistant Staphylococcus aureus infection) and confirmed diagnosis of indications for both tedizolid and linezolid (1: Deep Skin Infections, Chronic Abscesses, 2: Secondary infection of trauma, burns, and surgical wounds) in the same month or previous month of the index date. The disease code list is provided as Appendix A.

Index date is the first prescription date of tedizolid or linezolid observed in the cohort entry period (21-Aug-2018 to 31-Mar-2025). That is defined by using the prescription order in the SS-MIX2 data of the MID-NET dataset. New tedizolid prescription patients will be tedizolid group and new linezolid prescription patients will be linezolid group.

Diagnosis of MRSA and indications for tedizolid or linezolid are defined by using the disease name order in the SS-MIX2 data or DPC data or Administrative claims data of the MID-NET dataset.

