7.2.4 Participant follow-up

The follow-up will begin on the day after the index date.

The follow-up end date will be defined as the date of treatment period end, date of death, the end of the study period, start date of other treatment drug, or date of outcome onset whichever comes first. The date of death means recorded in SS-MIX2 as “date of death” or “death” in the hospital visit information summary or recorded in the DPC file as “death” in the discharge summary. If discrepancies in the date of death are found between SS-MIX2 and DPC, preference is given to the DPC data. If the date of death is missing in the DPC data, the missing information will be supplemented using the SS-MIX2 data, if available.

[figure not shown]
Switching of the medication from one treatment group to another (from tedizolid to linezolid group or vice versa) or an addition of the other medication will also be considered as a termination of the initial treatment, and patients will be censored on the day of termination of the initial treatment, which will be operationally defined as the start of another treatment per

| | |
|---|--|
| PRODUCT: MK-1986 | PROTOCOL/AMENDMENT VERSION NO.: 1986-047-00-V3 |
| REVOPS ID NO: NIS106696 EPIDEMIOLOGY NO.(PE STUDIES ONLY): EP08063.004 | NIR DRC APPROVAL DATE: NOVEMBER 25, 2025 |

the database. Note, the additional date (date when another medication is added) and the switching date (overlapping treatment date) are included in the follow-up period.

Note, the previous feasibility study shows the median time to discontinuation of initial treatment as **CC1** days.

Figure 2: Follow-up Schema

a. the treatment period end, date of death, the end of study period, start date of other treatment drug, date of outcome onset, whichever comes first.

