7.2.5 Longitudinality

This is a longitudinal surveillance. Factors to be considered in describing the clinical course of each patient are as follows:

1. All patients must have 60 days history before the index date (Lookback period).
2. The treatment period (continuous prescription period) for the tedizolid and linezolid groups is defined as from the index date to the end date of the last prescription period + grace period - 1.

A prescription period will be defined as prescription date + number of day's supply - 1.

| | |
|---|--|
| PRODUCT: MK-1986 | PROTOCOL/AMENDMENT VERSION NO.: 1986-047-00-V3 |
| REVOPS ID NO: NIS106696 EPIDEMIOLOGY NO.(PE STUDIES ONLY): EP08063.004 | NIR DRC APPROVAL DATE: NOVEMBER 25, 2025 |

The gap period is defined as the period from the end of the prescription period to the start of the next prescription period.

If the gap period is <14 days, the prescription periods are considered to be continued, and the prescription periods are consolidated. If the gap period is ≥ 14 days, the prescription periods are not consolidated, and the prescription periods after the gap period are not included in the analysis.

The gap periods for primary analysis are set at 14 days for tedizolid and linezolid based on the results of the feasibility study. It showed that the median gap period in the 1st use was [redacted] days for tedizolid group and [redacted] days for linezolid group. However, an analysis with a gap period of 7 days was also conducted as a sensitivity analysis (see Section 7.8.3 (3)). In addition, the feasibility study showed that the percentage of injections used was quite high (55/62 (88.7%) for tedizolid group and 476/574(82.9%) for linezolid group). Since most of the medication was injectable, the possibility of residual medication was considered to be low, and unnecessary to set a gap period longer than 14 days. In this study, this definition will be used as a common definition for tablets and injections. Also, it was considered unnecessary to set different treatment periods for injectable and oral agents.

The grace period is defined as the duration during which the effects of the drug may still be present, considering residual medication. It is considered the period that is added to the end date of the last prescription period. In this study, the grace period is set to be the same length as the gap period.

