7.3.2 Outcomes

The outcomes of interest in the study are peripheral neuropathy and optic nerve disorder.

Peripheral neuropathy is defined as cases meeting the following two conditions.

| | |
|---|--|
| PRODUCT: MK-1986 | PROTOCOL/AMENDMENT VERSION NO.: 1986-047-00-V3 |
| REVOPS ID NO: NIS106696 EPIDEMIOLOGY NO.(PE STUDIES ONLY): EP08063.004 | NIR DRC APPROVAL DATE: NOVEMBER 25, 2025 |

1. A confirmed diagnosis of peripheral neuropathy (ICD-10 code).
2. In the same month as, the month prior to, or the month after the confirmed diagnosis of peripheral neuropathy, a treatment drug for peripheral neuropathy or pain was prescribed, a test related to peripheral neuropathy was performed, or blood purification therapy for immune neuropathy was performed.

Optic nerve disorder is defined as cases meeting the following two conditions.

1. A confirmed diagnosis of optic nerve disorder (ICD-10 code).
2. In the same month as, the month prior to, or the month after the confirmed diagnosis of optic nerve disorder, vitamin B12 or corticosteroids were prescribed, or any of the relevant tests for optic nerve disorder (general, outpatient, or imaging tests) were performed.

The first event that meets any of the above definitions will be used for the analysis. The outcome occurrence date will be the earliest of the following: for Peripheral neuropathy, the prescription date of treatment drugs, the implementation date of blood purification therapy, or the test date; for Optic nerve disorder, the prescription date of treatment drugs or the test date.

Sensitivity analysis with variations of the about outcome definition regarding tests and treatment is detailed in Section 7.8.3 (7).

Although previous studies used ICD-9 codes to investigate peripheral neuropathy or ischemic optic neuropathy (7, 8), the codes identified in the literature might not be specific to the outcome in this study. Also, since there are no established diagnostic guidelines in Japan for peripheral neuropathy and optic nerve disorders, these definitions were established based on Japanese medical textbooks (9, 10) and Merck Manual Professional Version (11-15).

In addition, the above definition has been confirmed by medical doctor, and since there may be cases where tests and treatment drugs are not administered, an analysis using only diagnostic codes will be performed as a sensitivity analysis (see section 7.8.3 (8)).

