7.5 Study Size

The incidence of adverse events related to peripheral neuropathy and optic nerve disorder in the international Phase III clinical trials (Studies TR701-112 and 113) was 1.2% (8/662 patients) and 0.3% (2/662 patients), respectively. Based on this consideration, the incidence of an event in the tedizolid was assumed to be 0.3% to 1.2%.

[figure not shown]
Based on the results of the feasibility study, the median continued prescription period for tedizolid was **CCI** days, with a 75% tile of **CCI** days. From the above, a follow-up period of about 30 days was assumed.

According to the results of the MID-NET survey, there were **CCI** cases of patients prescribed tedizolid with confirmed diagnosis of MRSA during the period from May 2018 to March 2025. Considering the loss of cases due to exclusion criteria, it is estimated 100-200 patients will be included in the study.

Under this assumption, the power is shown below (Fig. 3) when the risk ratio (rate ratio) is set between 1.2 and 5.0 and the sample size of the tedizolid group is varied in 20 increments from 100 to 200 of the predicted accumulation. Note that sample size of the control group (linezolid) was assumed to be approximately 10 times that of the tedizolid group. A generalized linear model assuming Poisson distribution was used to detect group differences.

Figure 3: Power at each sample size assuming an event incidence rate of 1.2% and a risk ratio of 1.2-5 in the tedizolid group

| | |
|---|--|
| PRODUCT: MK-1986 | PROTOCOL/AMENDMENT VERSION NO.: 1986-047-00-V3 |
| REVOPS ID NO: NIS106696 EPIDEMIOLOGY NO.(PE STUDIES ONLY): EP08063.004 | NIR DRC APPROVAL DATE: NOVEMBER 25, 2025 |

For each condition, there was no sample size required for Power to be greater than 80%.

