 3. In the same month as, the month prior to, or the month after the confirmed diagnosis of peripheral neuropathy, a test related to peripheral neuropathy was performed.
Optic nerve disorder is defined as cases meeting all of the following three conditions:
 1. A confirmed diagnosis of optic nerve disorder (ICD-10 code).
 2. In the same month as, the month prior to, or the month after the confirmed diagnosis of optic nerve disorder, vitamin B12 or corticosteroids were prescribed.
 3. In the same month as, the month prior to, or the month after the confirmed diagnosis, any of the relevant tests for optic nerve disorder (general, outpatient, or imaging tests) were performed.
The first event that meets any of the above definitions will be used for the analysis. The outcome occurrence date will be the earliest of the following: for peripheral neuropathy, the prescription date of treatment drugs, the implementation date of blood purification therapy, or the test date; for optic nerve disorder, the prescription date of treatment drugs or the test date.

| | |
|---|--|
| PRODUCT: MK-1986 | PROTOCOL/AMENDMENT VERSION NO.: 1986-047-00-V3 |
| REVOPS ID NO: NIS106696 EPIDEMIOLOGY NO.(PE STUDIES ONLY): EP08063.004 | NIR DRC APPROVAL DATE: NOVEMBER 25, 2025 |

8) The analysis will be conducted with the following changes to the outcome definition.

Peripheral neuropathy is defined as cases meeting the following condition:

1. A confirmed diagnosis of peripheral neuropathy (ICD-10 code).

Optic nerve disorder is defined as cases meeting the following condition:

1. A confirmed diagnosis of optic nerve disorder (ICD-10 code).

The first event that meets any of the above definitions will be used for the analysis. The outcome occurrence date will be set as the last day of the month of the confirmed diagnosis.

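### Sensitivity analysis 8 dates code-only diagnoses at month end, which puts about half of on-treatment diagnoses after a 30-day follow-up and moves pre-index ones into it

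*Protocol*

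**What the plan says.** Protocol 7.3.2 explains that some cases may have neither a test nor a drug on record, and so "an analysis using only diagnostic codes will be performed as a sensitivity analysis (see section 7.8.3 (8"). Section 7.8.3 (8) then defines both outcomes by a confirmed ICD-10 diagnosis alone and adds: "The outcome occurrence date will be set as the last day of the month of the confirmed diagnosis".

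The risk window is set in 7.2.4: "The follow-up will begin on the day after the index date", and "The follow-up end date will be defined as the date of treatment period end, date of death", or at study end, start of the other drug, or outcome, whichever is first. Section 7.2.5 puts a grace period inside the treatment period: "The gap periods for primary analysis are set at 14 days for tedizolid and linezolid" and "In this study, the grace period is set to be the same length as the gap period". On length, 7.5 says: "From the above, a follow-up period of about 30 days was assumed". The median and 75th percentile behind that figure are redacted.

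Exclusion criterion 3 (7.2.3) removes patients with a prior event in the 60-day lookback, using the 7.3.2 definition. That definition needs a drug, test or procedure and takes its date from that record.

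The protocol gives no rule for a diagnosis whose assigned date falls after follow-up ends, and none for a diagnosis made earlier in the index month.

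**The concern.** A rule that can shift a date by up to a month is applied to a risk window of about a month. Take an index date of 20 April and 30 days of follow-up, so the window is 21 April to 20 May. A code recorded on 10 May, on treatment, is dated 31 May and falls outside. A code recorded on 5 April, before the drug was started, is dated 30 April and falls inside.

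This is the only planned analysis that loosens the outcome definition, and 7.10 concedes that the algorithms may not have optimal sensitivity, specificity or predictive value. If it discards many of the cases it was added to find and admits prevalent ones instead, its agreement or disagreement with the primary result says little about how well the outcome is captured.

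**Working it through.** **Inputs**
- Event date: last day of the diagnosis month (7.8.3 (8)).
- Window: index date + 1 to index date + L (7.2.4), capped at 31-Mar-2025.
- L: about 30 days (7.5). It cannot be rebuilt from its redacted inputs, so a range is shown.
- Index date: any day from 21-Aug-2018 to 31-Mar-2025 (7.2.2), 2,415 days.
- Assumptions, not in the protocol: index dates uniform over those days; true diagnosis day uniform over follow-up.

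**Step 1: on-treatment diagnoses lost.** A diagnosis is lost if its month end is later than the end of follow-up. Every index date was enumerated. As a check, take an average month of M = 30.4 days. For L up to M, the share lost is about 1 − (L + 1)/(2M). At L = 30 this is 1 − 31/60.8 = 0.490, against 0.489 by enumeration. At L = 19 it is 1 − 20/60.8 = 0.671, against 0.670.

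**Step 2: pre-index diagnoses moved in.** For each index date, take day 1 of that month up to the day before index. These days are redated into follow-up if the month end falls after index and on or before follow-up end. The mean pre-index span is 14.8 days per patient.

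| L (days) | On-treatment share lost | Pre-index share redated into follow-up | True diagnosis-days kept per patient | Pre-index diagnosis-days moved in per patient |
|---|---|---|---|---|
| 19 | 67% | 82% | 6.2 | 12.2 |
| 21 | 64% | 86% | 7.6 | 12.8 |
| 30 | 49% | 93% | 15.2 | 13.8 |
| 45 | 33% | 93% | 30.1 | 13.8 |
| 60 | 24% | 93% | 44.8 | 13.8 |

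At 30 days, 13.8/(15.2 + 13.8) = 48% of the days on which a code would be counted lie before the drug was started.

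**Step 3: sensitivity of the loss figure.** If risk rises linearly with time on drug, the loss is 65% at 30 days and 50% at 45. If follow-up varies between patients with a mean of about 30 days, it is 41–46%.

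**Step 4: does exclusion criterion 3 catch the pre-index cases?** As written, it requires a supporting drug, test or procedure and uses that record's date. It therefore removes pre-index cases with such a record in the lookback and leaves code-only cases in. If the code-only definition were applied to the criterion instead, the month-end rule would date an index-month diagnosis on or after the index date, so it would still not fall in the lookback.

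**The case against.** **Scale.** This is one of eight sensitivity analyses. With 100–200 tedizolid patients and 0.3–1.2% incidence (7.5), 100 × 0.003 = 0.3 to 200 × 0.012 = 2.4 events are expected, and an odds ratio needs 10 per group. The result will almost certainly be descriptive, and 7.10 already warns that odds ratios are likely to be inconclusive. This stands. It limits the consequence but does not make the dating right.

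**Month resolution may be deliberate.** The protocol uses month windows elsewhere for diagnoses (7.2.2, 7.3.2), and claims diagnoses may carry only a month. The protocol does not give this as the reason, and 7.3.2 also lists SS-MIX2 illness orders as a diagnosis source. What stands is that no single-day convention is right for month-only records. Treating every index-month diagnosis as prevalent would set aside 49% of true on-treatment diagnoses at 30 days, the same loss as the present rule.

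**The size depends on redacted durations.** This also stands. It is unclear whether the 30 days includes the 14-day grace period. If it does not, follow-up is about 44 days and the loss about 33%.

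**Differential bias.** A reader might infer that the loss distorts the drug comparison because it depends on treatment length. The document gives no legible duration by drug, so this is not shown. Nor does it follow from the rule alone. Suppose, purely for illustration, 19 days on one drug and 26 on the other, an equal daily diagnosis rate before and after index, and no removals under criterion 3. The days counted are 6.2 + 12.2 = 18.4 and 11.5 + 13.7 = 25.2, a ratio of 0.73. The true ratio, 19/26, is also 0.73. Under those assumptions the total is about right, but its composition is wrong.

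**Conclusion.** The point holds for sensitivity analysis 8 only. Followed as written, the month-end rule dates about 49% of on-treatment diagnoses after follow-up at the protocol's own 30 days, with a range from 67% at 19 days to 24% at 60. It also redates 82–93% of pre-index days in the index month into follow-up at 19–30 days. The second effect is confined to patients without a supporting record in the lookback, and these code-only cases are the ones the analysis was added to capture.

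The figures rest on uniform index dates and uniform diagnosis timing, and the true durations are redacted, so they should be read as a range. The primary analysis is unaffected. Two stronger readings are not supported: that the rule biases one drug against the other, and that criterion 3 misses every pre-index case.

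**What to change.** In sensitivity analysis 8, use the recorded diagnosis date wherever the source holds one (SS-MIX2 is the candidate; the protocol does not say whether it does), for both the outcome and the prior-event exclusion. With exact dates neither error arises.

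Where only the month is known, replace the month-end rule with two reported counts, each event dated at the earlier of month end and follow-up end:
- (a) a first diagnosis in any month overlapping follow-up, including the index month;
- (b) only a first diagnosis in a month after the index month that overlaps follow-up.

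Report how many diagnoses are month-only and fall in the index month, since these separate (a) from (b).

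The cost is protocol wording, slightly more derivation, and a range instead of one estimate. Count (b) is not a strict lower bound: at 30 days it still admits about 14.5 post-follow-up diagnosis-days per patient, from the rest of the last month. Requiring the whole month to lie inside follow-up would avoid that but would keep only about 2% of on-treatment days at 30 days, so it is not a usable alternative. The report should state this limit.

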7.8.4 Missing value

Missingness in the baseline covariates will be presented in tables. As most of the baseline covariates are defined as being present when there are corresponding diagnoses / prescriptions on record, there will be no missingness for these variables (those lacking the records will be considered as not having the condition). Missingness in other variables (e.g., age, sex) is possible, and will be handled appropriately depending on their size and suspected cause. Special consideration for outliers are not planned.

7.9 Quality Control

All parties agree to following applicable standard operating procedures (SOPs). All parties also agree to ensuring all existing and new study personnel are appropriately trained to ensure the study is conducted and data are generated, documented, and reported in compliance with the protocol, Good Pharmacoepidemiology Practice (GPP), Good Pharmacovigilance Practices (GVP), and all applicable federal, state, and local laws, rules and regulations. All parties should maintain transparency and open communication in order to effectively manage the study and proactively mitigate any risks.

The Sponsor may conduct routine or for-cause audits to ensure oversight and conduct of the study are completed in accordance with the protocol, quality standards (e.g. GPP and GVP), and applicable laws and regulations. If a significant quality issue (SQI) is identified at any time during the conduct of the study, it must be escalated to the Sponsor immediately. A SQI is any issue with the potential to negatively impact, either directly or indirectly, the rights, safety and well-being of patients or study participants and/or the integrity of the data. In the event an audit or SQI results in corrective or preventive actions, all parties are estimated to appropriately implement the action plan in a timely manner.

7.10 Limitations of the Research Methods

The number of patients treated with tedizolid or linezolid are likely to be very small because of the low use of these medications, even before applying the inclusion and exclusion criteria (which requires a MRSA diagnosis and specific prior therapies). In addition, the treatment period for these cohorts will be relatively short. Given very small numbers (patients / patient years), a high-risk population, previous treatment with other MRSA drugs that could be

| | |
|---|--|
| PRODUCT: MK-1986 | PROTOCOL/AMENDMENT VERSION NO.: 1986-047-00-V3 |
| REVOPS ID NO: NIS106696 EPIDEMIOLOGY NO.(PE STUDIES ONLY): EP08063.004 | NIR DRC APPROVAL DATE: NOVEMBER 25, 2025 |

associated with peripheral neuropathy and optic nerve disorder that are diagnosed at a later time, and many concomitant medications that can also be associated with the peripheral neuropathy and optic nerve disorder, it is possible that rates may be higher than observed in clinical trials or that there will appear to be imbalances between the two cohorts (who are actually taking bioequivalent medications), etc. Therefore, assessment of OR is likely to be inconclusive and care must be taken in interpretation of the data and generalizability of the surveillance results. Also, if there are no events in either the tedizolid or linezolid group, the OR cannot be calculated. Crude OR should not be calculated with less than 10 events.

When estimating the marginal effect of rare exposure, results using PS methods could be biased (22). Logistic regression models generating PS with small number of patients in tedizolid group might suffer from convergence problems and unstable parameter/coefficients estimates, as limited data provide insufficient information for reliable model fitting (23). Additionally, when a treatment group is rare, this group of patients are likely to receive very large weights, and thus have a disproportionate influence on the analysis, which is suspected to be the case with tedizolid based on the feasibility assessment. As these patients represent only a small proportion of the target study population, their disproportionate influence on the analysis may affect the precision of the average marginal effect estimate (24).

The sensitivity analysis which further restricts the population is even more likely to be inconclusive. More details on the specific limitations which may affect the surveillance results and their interpretation are described below.

- MID-NET contains data mostly from secondary care hospitals. Hence, data from primary care settings is limited, which may cause selection biases and limit generalizability of the results to the general MRSA population.
- Another major limitation of MID-NET is that patients cannot be followed up if they receive care at other healthcare facilities that do not contribute to MID-NET due to lack of patient-level data linkages among hospitals. Event incidences (e.g., diagnoses, laboratory tests, death, etc.) that occur outside the 31 hospitals are not captured in MID-NET, even during the follow-up period.
- The frequency of some laboratory tests may be low and/or the proportion of abnormal values may be overestimated because normal routine lab tests from the community are not captured.
- Representativeness – MID-NET in this activity comprises only 31 hospitals. When the 31 hospitals have specific clinical practices or include specific patients, e.g. more secondary prevention patients, the surveillance population or the results may not represent the general MRSA patient population or practices in Japan. MID-NET is made up of major hospital groups (Kitasato University and Tokushukai Hospital) and university hospitals. The patients prescribed tedizolid per the label may not be representative of all patients who take tedizolid (e.g., we know that some patients will not have a MRSA diagnosis, or may switch from a drug where switching is not specified in the JPC).

| | |
|---|--|
| PRODUCT: MK-1986 | PROTOCOL/AMENDMENT VERSION NO.: 1986-047-00-V3 |
| REVOPS ID NO: NIS106696 EPIDEMIOLOGY NO.(PE STUDIES ONLY): EP08063.004 | NIR DRC APPROVAL DATE: NOVEMBER 25, 2025 |

- Validity of outcome definitions – there is not a consensus on the best algorithms for defining the peripheral neuropathy and optic nerve disorder overall or specifically in Japanese databases. The algorithms that do exist may not have optimal sensitivity, specificity, and positive predictive value.
- Age, some comorbidities, some prior/concomitant drugs, etc. could affect risk of peripheral neuropathy and optic nerve disorder which is why we will examine demographic and clinical characteristics of the 2 groups as well as characteristics of drug utilization (e.g., duration of treatment, duration of follow-up, reasons for censoring). If there are differences in compliance / censoring, this could also affect the rates of peripheral neuropathy and optic nerve disorder and limit interpretation of the results. Therefore, a nominal elevation of OR may be seen due to imbalance of these factors, which needs to be taken into account in interpretation of the results and potentially limits generalizability.
- Residual confounding may persist despite efforts to adjust for measured covariates. Small sample size might also limit our ability to sufficiently control for confounding. We will discuss this limitation and the potential direction and magnitude of residual confounding in the final study report. Selection bias - tedizolid is a newly approved drug and could alert the prescribing physicians to monitor the patient more closely, resulting in enhanced capture of adverse events compared to the linezolid. This may lead to an overestimation of the risk for tedizolid.
- The disease diagnoses used to define covariates may be recorded for the purposes of claims, and coded diagnoses can be inaccurate and may lead to residual confounding.
- The database will only provide data on the prescription (and some dispensation data) for the medications. The actual use of the medication is not guaranteed and misclassification bias is possible. However, we don't expect this misclassification to be different in nature between the two exposure drugs and likely to be non-differential.

